### 14.5.1.5 Safety Laboratory

The following safety laboratory parameters will be determined:

#### Hematology

- RBC
- WBC
- Platelet count
- Hemoglobin
- Hematocrit

### Clinical chemistry

- aspartate aminotransferase
- alanine aminotransferase
- γ-glutamyltransferase

- alkaline phosphatase
- total bilirubin
- creatinine
- urea
- potassium
- sodium
- calcium
- chloride

#### Urinalysis

- pH
- Qualitative investigation for
  - pH
  - blood
  - white blood cells
  - protein
  - glucose
  - ketone bodies
  - nitrite
  - bilirubin
  - urobilinogen

Time points for the assessment of safety laboratory parameters are given in the study flow charts (see **section 3**).

# PART I

In part I, safety laboratory parameters are to be determined:

- In Adults: at screening visit, on PK dosing day 0 pre-dose of BT524 IV infusion, and on the follow-up days 1, 2, 4, 7, 10, and 14 post-infusion (see study flowchart for pharmacokinetics, **section** 3.1).
- In Children/Adolescents Group I and Group II: at screening visit, on PK dosing day 0 pre-dose of BT524 IV infusion, and on the follow-up days 1, 2, 7, and 14 post-infusion (see study flowchart for pharmacokinetics, **section 3.2 and 3.3**).
- In Pre-school Children Group III: at screening visit, on PK dosing day 0 predose of BT524 IV infusion, and on the follow-up day 2 post-infusion (see study flowchart for pharmacokinetics, **section 3.4**).
- In Newborns/Infants and Toddlers Group IV: at screening visit (biochemistry and urine analysis), and on PK dosing day 0 pre-dose of BT524 IV infusion (hematology). Additional determinations (hematology and biochemistry) on the follow-up day 1 (24 hours post-infusion) are to be performed only in infants and toddlers (see study flowchart for pharmacokinetics, **section 3.5**).

### PART II

On-demand prophylaxis/ on-demand treatment

 Without hospitalization: safety laboratory parameters are to be determined at screening visit (only for additional patients without participation in PK/PD part I) and on the dosing day 0 pre-dose of BT524 IV infusion, before discharge, and at each optional visit as required. • With hospitalization: safety laboratory parameters are to be determined at screening visit (only for additional patients without participation in PK/PD part I) and on the dosing day 0 pre-dose of BT524 IV infusion and as required post-end of infusion, at 24 hours post-end of infusion as required, from day 2 until the day before hospital discharge as required, on the day of hospital discharge as required, and at each optional visit as required. In all cases, they are to be determined at least once after the last infusion of BT542 and before discharge.

Safety laboratory parameters will be determined at the local laboratory. Details on collection, processing and handling of blood samples are described in the laboratory manual.

All safety laboratory blood and urine samples will be tested on an ongoing basis and will be destroyed after successful analysis.

### 14.5.1.6 Determination of Immunoglobulin Classes in Case of Anaphylaxis and/or Inhibitor Development

Immunglobulin E is to be determined in Adults and Children/Adolescents Group I and Group II ( $\geq$  6 years) on PK dosing day 0 pre-dose of BT524 IV infusion. In any patient developing anaphylaxis and/or inhibitors to fibrinogen, data on IgE against fibrinogen will be determined and recorded.

## 14.5.1.7 Ultrasonography Imaging

The ultrasonography is an imaging technique used in the study to visualize thromboembolic events (e.g., deep vein thrombosis). Detailed instruction on the performance of the ultrasonography will be provided in the ultrasonography guidance manual.

## PART I

In part I, ultrasonography imaging will be performed at screening visit, during the 14 day pharmacokinetic sampling period assessment whenever a thrombosis or TEE is suspected, and on follow-up day 14 (see study flowcharts for pharmacokinetics, **section 3**).

## PART II

On-demand prophylaxis/ on-demand treatment

- Without hospitalization: ultrasonography imaging are to be performed at screening visit (only for additional patients without participation in PK/PD part I) and on the dosing day pre-dose, post-end of infusion whenever a thromboembolic event is suspected, and at the safety visit if a thrombosis or TEE is suspected.
- With hospitalization: ultrasonography imaging are to be performed at screening visit (only for additional patients without participation in PK/PD part I) and on the dosing day pre-dose and from post-end of infusion until day of hospital discharge whenever a thrombosis or TEE is suspected.

### 14.5.1.8 Electrocardiogram (ECG)

### PART I

Standard ECG assessments are to be performed at screening visit, on PK dosing day 0, 6 hours post-end of BT524 IV infusion, and on follow-up day 1 (see study flowcharts for pharmacokinetics, **section 3**). The ECG print outs are signed by the investigator (= source document) and placed in the patient's chart.

### PART II

Standard ECG assessments are to be performed at screening visit only for additional patients without participation in PK/PD part I.

## 14.5.1.9 Pregnancy Test

### PART I

In all women of childbearing potential a negative pregnancy test (test sample either from urine) must be available at screening visit, on PK dosing day 0 pre-dose of BT524 IV infusion and on the follow-up day 14 (see study flowchart for pharmacokinetics, **section 3**).

#### PART II

In part II, a pregnancy test (urine) must be confirmed negative before each elective surgery and/or bleeding event on screening visit (only for additional patients without participation in PK/PD part I) and on dosing day 0 pre-dose. At each optional visit and at the safety visit (in case of a prematurely withdrawn from study participation) a further pregnancy test (urine) will be performed.

### 14.5.1.10 Viral Safety

Several pre- and post-dose serum samples (5 ml each) are to be taken from each patient participating in the study. The samples are to be collected and stored at -70 °C for possible future testing. Sample collection and processing are described in the laboratory manual.

### PART I

A serum sample is to be drawn on PK dosing day 0 pre-dose of the BT524 IV infusion for analysis, and as retention sample. At the safety visit, a serum sample is to be drawn as retention sample (day 49±4 after the administration of BT524).

### PART II

On-demand prophylaxis/ on-demand treatment

- Without hospitalization: a serum sample is to be drawn on dosing day pre-dose and at each safety visit (day 49±4 after the last administration of BT524).
- With hospitalization: a serum sample is to be drawn on dosing day pre-dose and at each safety visit (day 49±4 after the last administration of BT524).

#### 14.5.1.11 Retention Samples

All retention samples collected for local or central determination or for possible future testing (e.g., suspected transmission of an infective agent) will be destroyed after successful analysis, if applicable and finalization of the study report. This applies also for laboratory samples described in the efficacy chapter (refer to **sections 14.4.3.1** and **14.4.5**).

### 14.5.1.12 Assessment of Risk and Burden in Newborns, Infants and Toddlers, Children and Adolescents

At each study visit the investigator will assess and document whether the risk and burden imposed on each paediatric patient (0 to < 18 years) by participation in the study are acceptable. This has to be documented on a separate form.

### 14.5.2 Methods for Assessing, Recording and Analyzing Safety Parameter(s)

All laboratory results have to be evaluated in the eCRF according to the following pattern:

- a) outside reference range but not clinically relevant (e.g. due to already known conditions, due to sampling conditions, only marginal deviation, due to underlying diseases in the study population)
- b) outside reference range and clinically relevant.

Laboratory values which are outside the reference range and assessed as clinically relevant have to be controlled and documented as adverse events if they occur for the first time after administration of investigational medicinal product BT524.

If abnormal laboratory values are signs of an adverse event (e.g. an infection) that has already been reported during the present study, this has to be stated but the respective abnormal laboratory value does not constitute a separate adverse event.

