# 14.5.1.1 Adverse Events

Safety issues will be addressed by occurrence, frequency, nature, and severity of adverse events (AEs).

The number of AEs will be documented including safety laboratory parameters reported as adverse events.

The patients are asked about AEs during the infusion and since the last visit. The patients will furthermore be explicitly inquired with regard to their well-being by 'non-leading' questions at each visit.

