### 14.6 Adverse Events

14.6.1 Definitions

### Adverse Event (AE)

Any unfavorable or unintended sign, symptom, or disease that appears or worsens in a patient or clinical investigation subject during the period of observation in a clinical study. The AE may be any of the following:

- A new illness
- An exacerbation of a sign or symptom or the underlying condition under treatment or of a concomitant illness
- Unrelated to participation in the clinical study or an effect of the study medication or comparator drug
- A combination of one or more of the above factors

No causal relationship with the study medication is implied by the use of the term "adverse event".

Planned or elective surgical or invasive procedures for pre-existing conditions that have not worsened are not AEs.

However, any complication that occurs during a planned or elective surgery is an AE. Conditions leading to unplanned surgical procedures may be AEs.

When an AE occurs after written consent has been obtained but before the first dose of study drug, the AE will be considered a non-treatment emergent AE. An AE that occurs from the time the subject/patient receives his/her first dose of study drug until his/her last study visit will be considered a treatment emergent AE (TEAE).

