### Period:

• Patient Enrolment to the First Administration of Study Drug: Non-treatment emergent AEs will be recorded from the time when the patient is enrolled into the study (date of signature of the informed consent) until first administration of study drug.

- After Administration of Study Drug until respective 49 day visit (Part I and Part II): All TEAEs will be recorded.
- **In-between individual 49 day periods or after last 49 day visit:** Any serious treatment emergent AE considered to be related to the study medication by the investigator will be recorded.

If an AE (serious or not) started after administration of study drug but did not end before the 49 day visit, the investigator should make a reasonable effort to establish the outcome and the end date. If this is not possible, the outcome recorded at the 49 day visit will be assumed to be the final outcome.

If an event stops and later restarts, all the occurrences must be reported. AEs assessed as related to study medication by the investigator and all SAEs must be followed up until resolution.

The investigator should attempt to establish a diagnosis of the event based on signs, symptoms and/or other clinical information. In such cases, the diagnosis should be documented as the AE and/or SAE and not the individual signs/symptoms. Signs/ symptoms should be documented only if a diagnosis cannot be established. If a diagnosis is accompanied by unusual symptoms, the diagnosis itself and the symptoms have to be reported separately.

In addition to the definition as given, the following special types of events should be recorded:

Laboratory values that are outside the normal range and if, in the opinion of the investigator, these values represent a clinically relevant change versus pre-treatment values are also defined as AEs.
 If abnormal laboratory values are signs of an AE (e.g. an infection) that has

If abnormal laboratory values are signs of an AE (e.g. an infection) that has already been recorded, the respective abnormal laboratory value does not constitute a separate AE. Wherever reasonable the reporting investigator will use the clinical term rather than the laboratory term (e.g., anemia versus low hemoglobin value).

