11.1 Adverse events

All assessments will be done for all patients, part I and part II separately.

Adverse events (AE) will be coded using the MedDRA® dictionary. The current version will be used at time of database lock and presented by primary System Organ Class (SOC) and Preferred Term.

The analysis will focus on the treatment-emergent AEs (TEAEs). When an AE occurs after written consent has been obtained but before the first dose of study drug, the AE will be considered a non-treatment emergent AE. An AE that occurs (or worsened) on or after the time the patient receives his/her first dose of study drug (until his/her last study visit) will be considered a treatment emergent AE (TEAE). See also CSP section 14.6.2 for definition of non-treatment adverse events.

Please note the definition of study periods and adverse event reporting periods in section 5.5 above. Please also note that analyses for TEAE will be based on the safety population (SAF). Overview tables including non-TEAEs will be based on the APE to also include patients not treated in the study.

For the analysis of TEAEs only those TEAEs are taken into consideration which are reported from first treatment to the safety visit after treatment (independent of the planned duration between treatment start and Day 49 safety visit). For part I this is the duration between PK treatment and the Day 49 PK safety visit or earlier (if a bleeding event happened before Day 49 PK safety visit), and for part II this is for each bleeding event the duration between treatment of the bleeding event and Day 49 safety visit or earlier (if another bleeding event happened before Day 49 safety visit).

All other TEAEs reported out of these time frames will be counted and listed. Exception is the analysis of related serious adverse events (related SAEs) which are included in the analysis irrespective of the onset time after first administration of IMP:

If 'Day 49 safety visit' is not done, the period for inclusion of TEAEs in the analysis is from baseline (treatment start) to 49 days post-baseline.

The total number and percentage of patients reporting at least one AE and the absolute count of AEs will be tabulated for each age group and overall. This initial summary will be based on the APE set and provide a breakdown of the following:

- Any AE
- Any non-severe AE
- Any TEAE
- Any non-serious TEAE
- Any non-severe TEAE
- Any treatment-related TEAE
- Any severe AE

- Any severe TEAE

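### Protocol 14.5.2 and 14.6.2 apply different tests for when a laboratory value is an adverse event, and no text says which prevails

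*Protocol*

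**What the plan says.** Protocol 14.5.2 asks the investigator to sort out-of-range laboratory results into two groups: (a) not clinically relevant, for example because of a known condition or the underlying disease, and (b) clinically relevant. Group (b) values are to be rechecked and "documented as adverse events if they occur for the first time after administration of investigational medicinal product BT524".

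Protocol 14.6.2, on recording AEs, gives a second laboratory rule. It covers "Laboratory values that are outside the normal range" where, in the investigator's opinion, "these values represent a clinically relevant change versus pre-treatment values are also defined as AEs". There is no first-time condition. The same section says: "If an event stops and later restarts, all the occurrences must be reported".

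The general definition in Protocol 14.6.1 is "Any unfavorable or unintended sign, symptom, or disease that appears or worsens in a patient or clinical investigation subject". SAP 11.1 defines a TEAE as "An AE that occurs (or worsened) on or after the time the patient receives his/her first dose of study drug". The SAP has no laboratory AE rule of its own.

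Laboratory AEs enter the AE totals. Protocol 14.5.1.1 says: "The number of AEs will be documented including safety laboratory parameters reported as adverse events".

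**The concern.** The two laboratory rules do not refer to each other, and neither document ranks them. Section 14.5.2 is the one headed as the method for assessing and recording safety parameters, so a site could reasonably use it as its laboratory instruction and go no further. It would then apply a narrower test than 14.6.1, 14.6.2 and SAP 11.1.

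This bears mainly on part II. Exclusion criterion 8 bars clinically relevant haematology and biochemistry findings, but exempts those caused by the underlying disease or by an emergency bleed. Patients may also be treated for several events. TEAE figures could therefore depend partly on which section a site followed. An abnormality with no AE record also receives no severity, seriousness or causality assessment under Protocol 14.6.3.

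**Working it through.** The plan states no figure to reproduce, so the check applies each rule to each type of out-of-range value.

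| Before dosing | After BT524 | 14.5.2 read alone | 14.6.2 |
|---|---|---|---|
| Normal | First clinically relevant abnormality | AE | AE |
| Out of range, not clinically relevant (group a) | Becomes clinically relevant (group b) | AE, on a reasonable reading: first group (b) value | AE |
| Already clinically relevant | Clinically relevant worsening | Not an AE: not the first time | AE |
| Earlier clinically relevant abnormality, resolved | Recurs | Not an AE on a strict reading | AE, by the change rule and the restart rule |

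The rules agree in the first two rows and part in the last two.

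**Can the third row occur?** Yes, through the exemption in exclusion criterion 8. Protocol 14.5.1.3 itself notes that a deficit of factor I (fibrinogen) prolongs PT. The documents do not say how often any laboratory test is clinically relevant before a dose.

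**Which statistics move?** Protocol 15.2.6 defines AE incidence as the number and percentage of affected patients, and SAP 4.1.2.2 takes the patient as the unit for AEs. SAP 11.1 also tabulates the number of events.

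- *Worsening.* If it is the patient's only AE under a given term, omitting it lowers both the patient count and the event count.
- *Recurrence.* Assume probability p of the abnormality at each treated event, k independent events per patient, and no occurrence before BT524. Recording every occurrence gives kp events per patient on average. Recording only the first gives 1 − (1 − p)^k. The proportion of patients affected is 1 − (1 − p)^k under both rules, so only the event count changes.

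The documents give neither p nor k. For assumed values:

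- p = 0.1, k = 3: 0.30 v 1 − 0.9³ = 0.271; 0.029/0.30 = 10% fewer events.
- p = 0.2, k = 5: 1.00 v 1 − 0.8⁵ = 0.672; 0.328/1.00 = 33% fewer.
- p = 0.3, k = 8: 2.40 v 1 − 0.7⁸ = 0.942; 1.458/2.40 = 61% fewer.

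Patient incidence is not wholly protected. An abnormality that was present before BT524, resolved and came back could be left out altogether on the strict reading. One recorded in part I and recurring in part II could be absent from the part II tables, because the SAP assesses the parts separately.

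**What else would show these values?** SAP 11.8 gives summary statistics by visit, range categories, counts of values judged clinically significant, and an extra listing of those values. SAP 2.1 drops the laboratory shift tables that Protocol 15.2.6 had specified. No remaining planned table shows an individual's worsening from the pre-dose value.

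**The case against.** The best defence is that the rules are cumulative. Section 14.5.2 states a condition without saying it is the only one. Section 14.6.2 presents its laboratory rule as an addition to the AE definition and already requires every recurrence to be reported. A site reading both, with 14.6.1, would record worsening and recurrence. This reading is tenable, but the documents do not state it, and a site using 14.5.2 alone would not reach it.

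The gap is also narrow. A disease-related abnormality judged not clinically relevant before dosing becomes an AE under both rules once it turns clinically relevant. Exclusion criterion 8 keeps out many patients in the third row of the table, and eligibility is rechecked before each part II event. This limits the point without removing it, because the criterion has the two exemptions.

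SAP 11.8 reports clinically significant values whether or not an AE was recorded. This stands: the values are not lost to safety review. What can be lost is the AE record and its assessment.

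A reader might infer three stronger things that the documents do not support:

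- *All worsening from an abnormal pre-dose value is lost.* The second row of the table shows otherwise.
- *Part II laboratory AE rates are understated by a known percentage.* The percentages above rest on assumed p and k and concern event counts only.
- *Any omission flatters the product.* Omission lowers AE counts, but the events left out may have nothing to do with BT524.

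**Conclusion.** The inconsistency is real and should be corrected, though its reach is limited. Section 14.5.2 is out of step with 14.6.1, 14.6.2 and SAP 11.1, and no text settles which laboratory rule applies. The clear gap is a value already clinically relevant before dosing that then worsens; the less certain one is recurrence, where 14.6.2 gives the answer but 14.5.2 points the other way. The first can change patient-level TEAE incidence and event counts; the second mainly changes event counts.

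The size cannot be estimated. It depends on how many sites followed 14.5.2 alone, how often values were clinically relevant before dosing, and how many treated events each patient had, none of which the documents give. The conclusion rests on the wording alone and needs no assumed rate.

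**What to change.** In Protocol 14.5.2, replace the first-time condition with the 14.6.2 criterion: the value is out of range and is a clinically relevant new finding or worsening compared with pre-treatment, and all recurrences are reported. Cross-refer the two sections.

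State that in part II the reference is the pre-dose value of the same event. Section 14.6.2 does not say which pre-treatment value is meant; the same-event baseline is the one in SAP 11.8. Part II schedules no pre-dose biochemistry or urinalysis for children under 6 years, so say which earlier value, if any, serves for them.

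The SAP is dated 2 July 2020, after the data review meeting of 25 June 2020, so a change of wording may come too late to affect data collection. For data already collected, list the values that the investigator assessed as clinically significant, that are worse than the same event's pre-dose value, and that have no linked AE record. Query them before database lock; if the database is already locked, report the listing.

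The cost is a short text change, one listing from data already held, some queries, and possibly a few more laboratory AEs.

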### 14.6 Adverse Events

14.6.1 Definitions

### Adverse Event (AE)

Any unfavorable or unintended sign, symptom, or disease that appears or worsens in a patient or clinical investigation subject during the period of observation in a clinical study. The AE may be any of the following:

- A new illness
- An exacerbation of a sign or symptom or the underlying condition under treatment or of a concomitant illness
- Unrelated to participation in the clinical study or an effect of the study medication or comparator drug
- A combination of one or more of the above factors

No causal relationship with the study medication is implied by the use of the term "adverse event".

Planned or elective surgical or invasive procedures for pre-existing conditions that have not worsened are not AEs.

However, any complication that occurs during a planned or elective surgery is an AE. Conditions leading to unplanned surgical procedures may be AEs.

When an AE occurs after written consent has been obtained but before the first dose of study drug, the AE will be considered a non-treatment emergent AE. An AE that occurs from the time the subject/patient receives his/her first dose of study drug until his/her last study visit will be considered a treatment emergent AE (TEAE).

